Tedizolid is a FDA approved antibiotic with an indication for skin and soft tissue infection. Its spectrum of activity is nearly all gram positive cocci, i.e., the primary causes of osteomyelitis. Unlike the other commercially available medication in its class, linezolid, tedizolid does not appear to be associated with hematologic and neurologic toxicities in short term and animal studies. However, longer term studies with tedizolid have not been performed.

This study is a pilot study. We realize that efficacy is of primary concern for treatment of bone and joint infection, but the purpose of this study is more exploratory and will focus primary on the tolerability/toxicity issues outlined above.

Additional outcomes will be measured, but these are not primary outcomes. We will measure efficacy of tedizolid, but comparative efficacy (e.g., compared to non-tedizolid based regimens) will not be measured based on small sample size and funding limitations. Of great importance to highlight is that clinical trials, even non-comparative ones, are extremely rare for bone and joint infection. Randomized clinical trials comparing one antibiotic to another for bone and joint infection are almost never performed in the current era.

Hypotheses:

1. Tedizolid is well tolerated for prolonged (≥ 4 weeks) courses of antibiotic therapy for patients with bone and joint infection
2. Tedizolid is safe for prolonged (≥ 4 weeks) courses of antibiotic therapy for patients with bone and joint infection
3. Tedizolid is effective for the treatment of bone and joint infection

5) Background*

Describe the relevant prior experience and gaps in current knowledge.

Describe any relevant preliminary data.

Provide the scientific or scholarly background for, rationale for, and significance of the Human Research based on the existing literature and how will it add to existing knowledge.

PROTOCOL TITLE: *Tolerability, Safety, and Efficacy of Tedizolid as Oral Treatment for Bone and Joint Infection*

Revised: 8/10/18 Version 1.6

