The secondary study endpoint is the safety of prolonged (≥ 4 weeks) courses of tedizolid antibiotic therapy for patients with bone and joint infection. CBC and a CMP (comprehensive chemistry panel including liver function tests) will be performed at the following intervals after initiation of tedizolid. We will administer standardized surveys about drug side effects at all follow visits (weeks 1, 2, 3, 4, 5, 6 (optional), 7 (optional), 8 (optional), 9 (optional), 10 (optional), 11 (optional), 12). Adverse events will be measured using the Medical Dictionary for Regulatory Activities Terminology (MedDRA) version 18.1 (or the most current version).

The tertiary study endpoint is efficacy, which will be defined using criteria as determined by the subject's primary provider. Specifically, cure will be defined as no need for further antibiotics beyond the originally planned duration (i.e., 6 weeks for non-device associated bone and joint infection or until hardware removal for subjects with implants). Unplanned surgical procedures prompted by inadequate infection control will be categorized as treatment failure. We will also measure long-term efficacy by performing a phone survey 3 months after completion of antibiotics. Recurrence of signs or symptoms of bone and joint infection will be considered a long-term treatment failure. Confirmation of subjects self-report with medical record review will be performed on an as needed basis when categorization of self-reported outcomes is not clear.

g) Procedures Involved in the Human Research*

Describe and explain the study design.

The design of this study is a prospective, open-label, non-comparative clinical trial of tedizolid for the treatment of bone and joint infection. We will follow patients for between 16 and 24 weeks, depending on the length of their antibiotic treatment, for the purpose of determining tolerability, safety, and efficacy of prolonged use (≥ 4 weeks) of tedizolid in the treatment of bone and joint infection. Participants will be enrolled regardless of race, ethnicity, or gender (as long as they are within 18-85 years of age).

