At each follow up visit, CBC and CMP (comprehensive chemistry panel including liver function tests) will be collected via a blood draw. This blood sample will be sent to Quest Diagnostics by the

PROTOCOL TITLE: *Tolerability, Safety, and Efficacy of Tedizolid as Oral Treatment for Bone and Joint Infection*

Revised: 8/10/18 Version 1.6

CTSI/CTRU, an outside laboratory that is contracted with the CTSI/CTRU to process blood samples. Additionally, standardized surveys (See Data Collection Fields V 1.0, Neuropathy Scale V 1.0, attached) will be administered about drug side effects and tolerability, and adverse events will be measured using the Medical Dictionary for Regulatory Activities Terminology (MedDRA) version 18.1 (or the most current version). At these follow up visits, we will also record data points relevant to defining the efficacy of the treatment, such as the duration of the antibiotic treatment, any unplanned surgical procedures prompted by inadequate infection control, recurrence of signs or symptoms of bone and joint infection, and any other relevant comments or observations from the subject. The subject will also be asked to bring their study drug medication bottle and medication diary in order to assess compliance. If a subject suspects pregnancy during a follow up visit, they will be given a pregnancy test and the study team will track their reported menstrual cycle. If the subject does become pregnant, they will be discontinued from the study drug. Study staff will follow and collect data on the course of the pregnancy and the health of the child for at least 6-8 weeks after delivery.

Patients with evidence of myelosuppression will continue to have weekly CBCs performed until resolution of the myelosuppression.

Subjects who are concurrently taking serotonergic agents while receiving the study drug will be monitored for signs and symptoms of serotonin syndrome at each scheduled follow-up visit. Symptoms of serotonin syndrome include agitation or restlessness, confusion, rapid heartbeat and high blood pressure, dilated (big) pupils, loss of muscle coordination or twitching muscles, muscle rigidity (stiffness), heavy sweating, diarrhea, headache, shivering and goose bumps.

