Additionally, subjects may be withdrawn in the following circumstances development of significant cytopenias and liver function abnormalities, symptoms of neuropathy, gastrointestinal intolerance, or, in the opinion of the investigator, any new severe signs or symptoms that may be related to the study drug.

PROTOCOL TITLE: *Tolerability, Safety, and Efficacy of Tedizolid as Oral Treatment for Bone and Joint Infection*

Revised: 8/10/18 Version 1.6

If a subject becomes pregnant during the study, they will be discontinued from the study drug. Study staff will follow and collect data on the course of the pregnancy and the health of the child for at least 6-8 weeks after delivery.

Describe any procedures for orderly termination.

Termination of the study will occur based on the primary investigators judgment. Subjects will be provided referrals for their medical conditions, if needed.

Describe procedures that will be followed when subjects withdraw from the research, including partial withdrawal from procedures with continued data collection.

Subjects who withdraw from the study will be asked to notify the study team. No further visits will be required. Additionally, if a subject withdraws from the study, a member of the study team will contact their primary treatment physician and/or infectious disease consultant to ensure that the patient is given antibiotic therapy immediately upon discontinuation of study drug.

10) Risks to Subjects*

List the reasonably foreseeable risks, discomforts, hazards, or inconveniences to the subjects related the subjects' participation in the research. Include as may be useful for the HSC's consideration, describe the probability, magnitude, duration, and reversibility of the risks. Consider physical, psychological, social, legal, and economic risks.

According to the package insert for tedizolid (Sivextro), adverse reactions were evaluated for 1050 patients treated with tedizolid (200 mg oral/intravenous once daily for 6 days) in two Phase 2 and two Phase 3 ABSSSI (acute bacterial skin and soft structure infection) clinical trials. The median age of patients treated with tedizolid (200 mg oral/intravenous once daily for 6 days) in the Phase 2 and Phase 3 ABSSSI trials was 42 years, ranging between 17 and 86 years old. Patients treated with tedizolid (200 mg oral/intravenous once daily for 6 days) were predominantly male (65%) and white (82%).

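### The definition of cure does not require that tedizolid remained the Gram-positive agent, so a subject switched for inadequate response can meet it

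*Combined protocol and SAP*

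**What the plan says.** Hypothesis 3 in section 4) Objectives is that "Tedizolid is effective for the treatment of bone and joint infection".

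The tertiary endpoint in 9) f) Study Endpoints is "efficacy, which will be defined using criteria as determined by the subject's primary provider". The next sentence makes this specific: "cure will be defined as no need for further antibiotics beyond the originally planned duration". The planned duration is given as 6 weeks without a device, or until hardware removal with an implant. Two failure events follow. During treatment: "Unplanned surgical procedures prompted by inadequate infection control will be categorized as treatment failure". Later, through the phone survey three months after antibiotics end: "Recurrence of signs or symptoms of bone and joint infection will be considered a long-term treatment failure".

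Under 9) g) Procedures, the efficacy items recorded at visits are described by example, "such as the duration of the antibiotic treatment, any unplanned surgical procedures prompted by inadequate infection control", followed by recurrence and other comments. A change of antibiotic and its reason are not named.

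The section on Withdrawal of Subjects says "subjects may be withdrawn in the following circumstances development of significant cytopenias and liver function abnormalities", and goes on to neuropathy, gastrointestinal intolerance and severe events possibly related to the drug. Inadequate response is not on that list. After withdrawal no more visits are required, and the team contacts the treating physician to "ensure that the patient is given antibiotic therapy immediately upon discontinuation of study drug".

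Section 9) c) Local Number of Subjects enrols until 50 subjects are analyzable with all follow-up done through 12 weeks, and expects about 55 enrolled. Section 9) i) Data Management says that no formal statistical analysis plan exists.

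**The concern.** The hypothesis is about tedizolid, but the rule for cure is about total antibiotic time on any drug. Where another agent takes over within the planned period and succeeds, the rule can credit tedizolid with the result. Inadequate response managed by changing the drug, rather than by operating, leaves no trace in the endpoint.

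The study has no comparator against which a reader could notice or correct this. Section 9) i) also justifies the sample size partly as enough to reassure clinicians about efficacy, so the cure rate will be read as a property of tedizolid. Without a stated rule, switched subjects would be classified after their outcomes are known, in an open-label study.

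**Working it through.** **Step 1. Reproduce the plan's figure.** Section 9) i) anticipates 80% cure with n=50 and a 95% interval of 69% to 91%. The Wald interval is p ± 1.96 × √(p(1−p)/n). Here √(0.8 × 0.2/50) = 0.0566, and 1.96 × 0.0566 = 0.111. The interval is 68.9% to 91.1%, which matches. The plan's arithmetic is not at issue.

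**Step 2. Apply the written rule to a switch for inadequate response.** Take a subject planned for 6 weeks and changed to another Gram-positive agent at week 3.
- Inadequate response is not a listed ground for withdrawal, so the subject can stay in the study.
- Section 9) g) brings all subjects back at weeks 1 to 5 and week 12, so the subject can complete follow-up and count among the 50.
- Antibiotics end at week 6, so none are needed beyond the planned duration.
- There is no unplanned surgery.

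The written definition is met. A switch at week 5 gives the same result.

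**Step 3. Apply it to a stop for intolerance.** Two outcomes are open.
- *Withdrawn from the study:* no further visits are required, the subject does not complete 12 weeks, and a replacement is enrolled.
- *Drug stopped but still followed:* withdrawal is worded as something that may happen. The protocol elsewhere separates stopping the drug from ending observation: subjects who become pregnant stop the drug but are followed, and blood counts continue weekly after myelosuppression until it resolves. Such a subject can complete follow-up on a replacement antibiotic and meet the definition.

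**Step 4. Size if switched subjects are scored as cures.** Suppose 40 of 50 meet the written definition and k of those 40 were switched. The rate with switches as non-cures is (40 − k)/50. The documents give no value for k, so the range is an assumption.

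| k | Rate | Wald 95% interval |
|---|---|---|
| 0 | 80% | 68.9% to 91.1% |
| 1 | 78% | 66.5% to 89.5% |
| 3 | 74% | 61.8% to 86.2% |
| 5 | 70% | 57.3% to 82.7% |
| 10 | 60% | 46.4% to 73.6% |

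Each subject moves the rate by 1/50 = 2 points. Five move it by 10 points, close to the plan's half-width of 11.

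**Step 5. Size if stopped subjects are dropped and replaced.** Assume that 5 of 55 enrolled leave this way and that 40 of the remaining 50 are cures.
- Reported among completers: 40/50 = 80%.
- All 55, with the five as non-cures: 40/55 = 72.7% (61.0% to 84.5%), a gap of 7.3 points.
- All 55, with the five as cures: 45/55 = 81.8% (71.6% to 92.0%).

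The same five subjects can therefore move the rate over all 55 from 72.7% to 81.8%, and the plan does not say which treatment applies.

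**The case against.** The strongest reply is that the endpoint opens by leaving the criteria to the primary provider, who could class a change for non-response as failure. That weakens any claim of certainty. It does not remove the gap, because the sentence that follows supplies a specific definition. If providers may depart from it, switched subjects will be scored inconsistently.

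A reader might infer that every subject who leaves tedizolid early, including for toxicity, will be scored as a tedizolid cure. The documents do not support that. The withdrawal section and the completer requirement make removal and replacement a real possibility for intolerance, so those subjects may never enter the cure rate. That is a different distortion, and redefining cure alone would not reach it.

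It can also be said that subjects stopped before 4 weeks fall outside the study's interest in prolonged use. This may be the intention, but the term analyzable is not defined, and a switch after week 4 raises the same question.

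Some protection does exist. Antibiotics needed past the planned duration rule out cure, and later recurrence counts as long-term failure. Neither catches a subject in whom the replacement drug worked on time.

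Finally, efficacy is tertiary in a descriptive pilot that is not meant to support a labelling change, and no decision rule uses the cure rate. This stands, and it limits the severity.

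**Conclusion.** The point holds for subjects switched because of inadequate response: with no unplanned surgery and no antibiotics past the planned duration, they meet the written definition of cure. For subjects stopped for intolerance the plan leaves two routes open, scoring as cure or removal and replacement. Either can raise the reported rate relative to counting them as non-cures.

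The size is 2 points per switched subject at n=50, or 7.3 points if 5 of 55 are dropped and replaced. The numbers of subjects are assumptions. It would be wrong to say that the plan's 80% is itself inflated: it is an anticipated value used for planning, not a result obtained under this rule.

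This should be fixed, but it does not threaten the study's main purpose. The primary tolerability endpoint is unaffected.

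**What to change.** In 9) f):
- Define cure as completing the planned course with tedizolid as the Gram-positive agent, with no antibiotics beyond the planned duration and no unplanned surgery for inadequate infection control. Naming the Gram-positive agent keeps the rule compatible with inclusion criterion d), which allows other antibiotics aimed at other organisms.
- Score as failure any replacement or added Gram-positive agent given for inadequate response.
- Record the date and reason of any stop or switch of tedizolid.
- Report the cure rate with intolerance switches counted as non-cure, and again with them set apart.
- Give both results over all treated subjects as well as over the 50 completers. Counting intolerance switches as non-cure, or setting them apart, needs no further visits from subjects withdrawn for that reason.

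The cost is a paragraph of wording, one added data field and a possibly lower reported cure rate. The visit items listed in 9) g) do not name a switch or its reason, and concomitant medications are described as collected after consent. The attached data collection form is not in the documents, so whether it already holds this field cannot be checked. No treatment decision changes.

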defined clinically using radiologic (e.g., MRI) and/or surgical (e.g., intra-operative findings) definitions. All subjects must have confirmation (diagnosis mentioned in chart) by the patient's primary physician and consultants that the patients has or likely has bone and joint infection and requires prolonged antibiotic therapy.

- b) Aged between 18 years and 85 years.
- c) Plans to treat bone and joint infection in outpatient setting.
- d) No limited planned course of antibiotics. Co-administration of other antibiotics that target other causative or potentially causative organisms (e.g., fluoroquinolones) is acceptable.
- e) Able to come to the research clinic for study follow-up visits for the study period.

Exclusion criteria for subjects will include:

- a) Planned prolonged hospitalization (> 1 week).
- b) Pregnancy (all female subjects of childbearing age will be given a pregnancy test prior to enrollment) or breast feeding. If a woman is of childbearing potential, she must consistently use two acceptable methods of contraception (IUD, injectable contraceptive, birth control patch, OCP, barrier method, abstinence) from baseline through the course of antibiotics (4-12 weeks). If a male patient's sexual partner is of childbearing potential, the male patient must acknowledge that they will consistently use an acceptable method of contraception as defined above from baseline through the course of antibiotics (4-12 weeks).
- c) Comorbidities that, in the opinion of the investigator, are uncontrolled (e.g., diabetes, hypertension, psychiatric disease).
- d) Peripheral or optic neuropathy.
- e) Underlying hematologic cytopenias (e.g., baseline thrombocytopenia, or severe anemia, or leukopenia) as determined by the following limits from a baseline CBC/CMP obtained within the past 14 days. Note that if a CBC has not been performed within the past 14 days, a CBC will be performed on the day of enrollment prior to any study drug being administered to ensure the patient does not meet exclusion criteria. Cytopenias are defined as:
 - Hemoglobin (Hgb) \leq 8.0g/dL
 - WBC \leq 4,000 k/cumm
 - Platelets \leq 150,000 k/cumm

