Subjects will be given tedizolid orally 200 mg once daily for duration of therapy of between 4 and 12 weeks. The exact duration of tedizolid therapy will be decided by the subject's treating physician. In other words, the primary/consulting physician who is managing the treatment of the patient's bone and joint infection will be the one who decides the length of the tedizolid treatment.

Safety and tolerability of tedizolid through this study will be guaranteed for 12 weeks. Provision of tedizolid therapy beyond 12 weeks is not guaranteed by the clinical trial as excessively prolonged therapy is associated with increased monitoring cost (e.g., subject payments, laboratory tests, clinic utilization costs). If patients require greater than 12 weeks of therapy for Gram-positive pathogens, study

PROTOCOL TITLE: *Tolerability, Safety, and Efficacy of Tedizolid as Oral Treatment for Bone and Joint Infection*

Revised: 8/10/18 Version 1.6

staff will contact the subject's primary provider to arrange alternative oral or IV therapy. Medications will be provided by the Investigational Drug Service (IDS) on the LA BioMed/Harbor-UCLA campus, which supplies all research related medications to study subjects at our center.

Subjects will be enrolled as outpatients or as inpatients when discharge is expected in the near future (\leq 1 week). [name], the primary investigator, and his team will advise the hospital staff of the study and seek their assistance in identifying and notifying the study staff of possible subjects who have presented to the Emergency Department, Inpatient Floors, or Outpatient Clinic with bone and joint infection. The Investigator or study staff will approach the subject's primary treatment team and ask for their permission to introduce the study and the study staff to the patient. Study staff will then present information about the study (See Recruitment Script V1.0) to see if they are interested. Permission will be sought from the subject by their primary treatment team before anyone outside the patient's primary treating team approaches them about the study.

Once an interested patient is identified, study staff will explain the details of the study to the subject. If the patient is interested in participating, study staff will complete the informed consent process in a private setting in the patient's preferred language (English or Spanish).

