The subjects will be paid in cash for their follow up visits. They will be paid \$30 for the visit on week 1, \$35 for the visit on week 2, \$40 for the visit on week 3, \$40 for the visit on week 4, \$45 for the visit on week 5, \$45 for the visit on week 6, and \$50 each visit for visits on weeks 7, 8, 9, 10, 11, 12 and 13.

The total amount of compensation will range between \$240 and \$585 based on the number of follow up visits the subject completes. All subjects will complete visits on Weeks 1,2,3,4,5, and 12. Subjects still taking the study drug at week 6 will be required to return for a Week 6 follow up visit. Subjects still taking the study drug at week 7 will be required to return for a week 7 follow up visit, and so on- while patients are receiving the study drug they will return for weekly follow up visits until they have completed the course, or until they have reached 12 weeks. Once subjects complete the course of the study drug, they will return for one additional weekly follow up visit (e.g. if a patient completes the study drug at 7 weeks, they will return for visits on weeks 1-8 and week 12). If subjects take the study drug for 12 weeks, they will return for a final follow up visit on week 13.

A phone survey 3 months after the subject's completion of antibiotics will be performed. They will be asked about their overall well-being, recurrence of signs or symptoms of bone and joint infection and any self-reported medical conditions or adverse events (medical record review will be performed on an as needed basis when categorization of self-reported outcomes is not clear).

Provide a description of all procedures being performed and when they are performed, including procedures being performed to monitor subjects for safety or minimize risks. Include procedures

PROTOCOL TITLE: *Tolerability, Safety, and Efficacy of Tedizolid as Oral Treatment for Bone and Joint Infection*

Revised: 8/10/18 Version 1.6

being performed already for diagnostic or treatment purposes and differentiate between these and the procedures performed solely for the research.

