Because this study is using tedizolid for longer than the FDA approved duration, we have received an IND (133495) which was approved to proceed on 1/12/17. The study drug will be prescribed/administered as prolonged antibiotic therapy for a duration of time based on the judgment of the primary/consulting physician who is treating the subject's bone and joint infection.

19) Multi-Site Human Research*

Not Applicable – not a multi-site study.

If this is a multi-site study where you are the lead investigator, describe the processes to ensure communication among sites, such as:

- *All sites have the most current version of the protocol, consent document, and HIPAA authorization.*
- *All required approvals have been obtained at each site (including approval by the site's HSC of record).*
- *All modifications have been communicated to sites, and approved (including approval by the site's HSC of record) before the modification is implemented.*
- *All engaged participating sites will safeguard data as required by local information security policies.*
- *All local site investigators conduct the study appropriately.*
- *All non-compliance with the study protocol or applicable requirements will be reported in accordance with local policy.*

Describe the method for communicating to engaged participating sites:

PROTOCOL TITLE: *Tolerability, Safety, and Efficacy of Tedizolid as Oral Treatment for Bone and Joint Infection*

Revised: 8/10/18 Version 1.6

- *Problems.*
- *Interim results.*
- *The closure of a study*

20) Community-Based Participatory Research

Describe involvement of the community in the design and conduct of the research.

Note: “Community-based Participatory Research” is a collaborative approach to research that equitably involves all partners in the research process and recognizes the unique strengths that each brings. Community-based Participatory Research begins with a research topic of importance to the community, has the aim of combining knowledge with action and achieving social change to improve health outcomes and eliminate health disparities.

Not Applicable

21) Sharing of Results with Subjects

Describe whether results (study results or individual subject results, such as results of investigational diagnostic tests, genetic tests, or incidental findings) will be shared with subjects or others (e.g., the subject’s primary care physicians) and if so, describe how it will be shared.

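### Cure is tied to 6 weeks or hardware removal while the treating physician sets a 4–12 week course; which reference governs is not stated, and implant subjects still on antibiotics have no category

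*Combined protocol and SAP*

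**What the plan says.** **Cure definition.** Section 9 f) Study Endpoints says that efficacy, the tertiary endpoint, follows "criteria as determined by the subject's primary provider". The next sentence makes this specific: cure is "no need for further antibiotics beyond the originally planned duration (i.e., 6 weeks for non-device associated bone and joint infection or until hardware removal" in subjects with implants. Unplanned surgery because the infection was not controlled is a failure. Signs or symptoms that return by the follow-up call are a long-term failure.

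**Length of treatment.** Section 9 g) says: "Subjects will be given tedizolid orally 200 mg once daily for duration of therapy of between 4 and 12 weeks". It adds: "The exact duration of tedizolid therapy will be decided by the subject's treating physician". Section 18) Drugs or Devices repeats that the drug is given "for a duration of time based on the judgment of the primary/consulting physician". Neither section restricts the longer courses to implant subjects. Section 9 b) requires only that at least 4 weeks be planned. The visit schedule in 9 a) and 9 g) is illustrated by a subject who finishes study drug at 7 weeks.

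**After week 12.** If more than 12 weeks of therapy is needed, 9 g) says that "staff will contact the subject's primary provider to arrange alternative oral or IV therapy". It gives no outcome category for such a subject. On the call, 9 g) says: "A phone survey 3 months after the subject's completion of antibiotics will be performed". Section 9 e) puts total participation at 16 to 24 weeks.

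**Figures that rest on the definition.** Section 9 i) anticipates 80% cure with a 95% interval of 69%–91% at n=50. Section 9 c) enrols until 50 analyzable subjects have been followed through 12 weeks.

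**The concern.** The definition first ties cure to a plan and then, with an *i.e.*, states what that plan is: 6 weeks, or removal of the hardware. Elsewhere the plan is whatever the treating physician decides, and the protocol's own example is not 6 weeks. The two references disagree for any non-device subject whose planned course is longer than 6 weeks. For implant subjects, removal works as an end point only if it happens.

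Efficacy is in the title and is the third hypothesis. Section 9 i) presents n=50 as enough to reassure clinicians on efficacy as well as safety. In an open-label single-arm study, two assessors following the text could score the same subject differently. Subjects left without a category could be counted as cures, counted as failures or left out, and that choice could be made after outcomes are known. Tolerability, safety and the sample size do not depend on the cure definition.

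**Working it through.** **1. The plan's own figure.** Inputs from 9 i): p = 0.80, n = 50. The Wald 95% interval is 0.80 ± 1.96 × √(0.80 × 0.20 / 50) = 0.80 ± 0.111, or 68.9%–91.1%. This reproduces the stated 69%–91%, with a half-width of 11.1 points.

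**2. The two references side by side.** The 8-week plan is an illustration within the 4–12 week range.

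| Subject | Scored by the fixed durations in 9 f) | Scored by the physician's plan (9 g), 18)) |
|---|---|---|
| Non-device, planned 6 weeks, completed, no more antibiotics | Cured | Cured |
| Non-device, planned 8 weeks, completed, no more antibiotics | Not cured: antibiotics went past 6 weeks | Cured |
| Implant, hardware still in, still on antibiotics at week 12 | No result: removal has not occurred | Failed if past a finite plan; otherwise no result |

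Section 9 f) counts antibiotics, while 9 g) and 18) count tedizolid. The second row holds if the 6 weeks start no later than the first tedizolid dose, because a tedizolid course longer than 6 weeks then exceeds 6 weeks of antibiotics whatever was given before.

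**3. Whether the follow-up call settles the third row.** Take 3 months as 12 weeks. Then 4 + 12 = 16 weeks and 12 + 12 = 24 weeks, which is the participation range in 9 e). That range fits only antibiotic courses ending by week 12. For a subject whose antibiotics end later, the call falls after week 24; for one whose antibiotics do not end, it has no date.

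**4. Size.** The documents give neither the share of subjects with hardware nor the planned durations, so the counts below are assumptions that show the range.

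- One subject: 1/50 = 2 points.
- Reclassified cures, starting from 40/50: moving 2 gives 38/50 = 76%; moving 5 gives 35/50 = 70%.
- Unresolved subjects, u of 50, kept in the denominator: counting all as cures or all as failures differs by u/50. For u = 1, 5, 10 that is 2, 10, 20 points.

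If 80% of the resolved subjects are cured:

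| u (assumed) | Cured among resolved | Unresolved as failures (Clopper-Pearson 95%) | Unresolved as cures (Clopper-Pearson 95%) | Unresolved left out (Wald 95%) |
|---|---|---|---|---|
| 5 | 36/45 | 36/50 = 72% (57.5%–83.8%) | 41/50 = 82% (68.6%–91.4%) | 36/45 = 80% (68.3%–91.7%) |
| 10 | 32/40 | 32/50 = 64% (49.2%–77.1%) | 42/50 = 84% (70.9%–92.8%) | 32/40 = 80% (67.6%–92.4%) |

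The two columns with 50 as denominator apply only if unresolved subjects are among the 50.

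**The case against.** The strongest reply is that the sections can be read together: the provider's criteria and the physician's plan govern, and the parenthesis only names the usual plans. That reading is available. It is not stated, however, and the sentence that follows the reference to the provider replaces it with a specific rule introduced by *i.e.*, which restates a term and does not give an example. If the sponsor means the individual plan, deleting the parenthesis says so.

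Section 9 g) also has staff record antibiotic duration, unplanned surgery and recurrence at each visit. Clinical failure in a subject with retained hardware would therefore be seen, and much of the data for either reading is collected. This stands and keeps the cost of a fix low. It does not supply a category for a subject with none of these events who is still on antibiotics.

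Sections 9 c) and 9 d) speak of analyzable subjects with study outcomes, so an unresolved subject might be replaced. In that case the spread on a fixed denominator of 50 would not arise. Analyzable is not defined, so neither outcome is secure.

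Three stronger inferences are tempting, and the documents do not support them:

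- *A 4-week plan extended to 6 weeks would be scored as a cure.* This needs the 6 weeks of antibiotics and the tedizolid course to start together, which no section says.
- *Subjects have no finite plan at all*, from the inclusion criterion "No limited planned course of antibiotics". Beside the requirement that at least 4 weeks be planned, it more naturally excludes short courses.
- *The reported cure rate will be too high.* The long-course case lowers the rate under the literal text, while unresolved subjects could move it either way.

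**Conclusion.** The point holds for the tertiary efficacy endpoint. As written, the cure definition scores a non-device subject who completes a planned course longer than 6 weeks as not cured. It also gives an implant subject with hardware in place and antibiotics continuing no end point against which to be judged. No section says whether the fixed durations or the physician's plan governs cure, and none classifies subjects still on antibiotics when visits end.

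Neither the size nor the direction of any misclassification can be found from the documents. Each affected subject is worth 2 points on n=50. An assumed 10 unresolved subjects would open a gap of 20 points, close to the full planned interval width of about 22 points, but nothing in the documents says that the number is that large or that such subjects stay among the 50. This is a descriptive pilot, and a reader should not extend the point to tolerability, safety or the choice of n=50. No view is taken on treatment duration or hardware management.

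**What to change.** Reconcile sections 9 f), 9 g) and 18) by deleting the fixed durations from the cure definition. Score cure against each subject's planned total antibiotic duration, as set by the treating physician and recorded at enrolment with its start date, or recorded as open-ended. Apply these categories in order, to subjects with and without hardware:

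1. **Failure:** unplanned surgery because the infection was not controlled, or antibiotics for the infection continuing past a recorded finite plan.
2. **Unresolved:** still on antibiotics within the recorded plan, finite or open-ended, at the last in-person study visit (week 12 or 13).
3. **Cure:** antibiotics ended with no need to go beyond the plan.

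Keep recurrence at the 3-month call as long-term failure, with the call still timed from the end of antibiotics. Report unresolved subjects separately, keep them in the denominator, and give a sensitivity result counting them as all cures and as all failures.

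The cost is endpoint wording and, if the data collection form (not seen) lacks them, one or two baseline fields. The reported cure rate may look less favourable. There are no extra visits or calls, and no subject's treatment changes.
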